#### **4.3. Exclusion Criteria**

Subjects who meet *any* of the following exclusion criteria are not to be enrolled in this study.

- 1) Receipt of an HCV infected liver
- 2) Any serious or active medical or psychiatric illness which, in the opinion of the investigator, would interfere with subject treatment, assessment, or compliance
- 3) HIV infection or a positive hepatitis B virus surface antigen result
- 4) Current malignancy (with exception of HCC within local listing criteria, certain resolved skin cancers or other early cancer for which surgical resection is considered to be completely curative)
- 5) Treatment with any approved or experimental medication with known anti-HCV activity within 1 month prior to screening date
- 6) Prior exposure to a HCV NS5B nucleotide/side inhibitor including SOF or to an HCV NS5A inhibitor
- 7) Patients on hemodialysis prior to or at the time of transplantation will be excluded
- 8) Participation in a clinical study with an investigational drug or biologic within 28 days prior to screening visit, unless information on the investigational drug is available to indicate that there is no potential drug interaction (safety or efficacy)
- 9) Use of any prohibited concomitant medications as described in Section 5.3. Known hypersensitivity to the SOF, VEL, the metabolites, or formulation excipient.

## **5. INVESTIGATIONAL MEDICINAL PRODUCTS**

### **5.1. Description and Handling of SOF/VEL FDC**

#### **5.1.1. Formulation**

The SOF/VEL (400 mg/100 mg) FDC tablets are pink, diamond-shaped, film-coated tablets, debossed with “GSI” on one side and “7916” on the other side. In addition to the active ingredients, the SOF/VEL tablets contain copovidone, microcrystalline cellulose, croscarmellose sodium, magnesium stearate, polyvinyl alcohol, titanium dioxide, polyethylene glycol, talc, and iron oxide red.

#### **5.1.2. Packaging and Labeling**

SOF/VEL (400 mg/100 mg) FDC tablets are packaged in white, high density polyethylene (HDPE) bottles. Each bottle contains 28 tablets and polyester packing material. Each bottle is enclosed with a white, continuous thread, child-resistant screw cap with an induction-sealed, aluminum-faced liner.

SOF/VEL bottles to be distributed to centers in participating countries shall be labeled to meet all applicable requirements of the United States Food and Drug Administration (FDA), EU Guideline to Good Manufacturing Practice - Annex 13 (Investigational Medicinal Products), and/or other local regulations.

#### **5.1.3. Storage and Handling**

SOF/VEL FDC tablets should be stored at controlled room temperature until required for administration. Controlled room temperature is defined as 25°C (77 °F); excursions are permitted between 15°C and 30°C (59°F to 86°F).

All drug products should be stored in a securely locked area, accessible only to authorized site personnel. To ensure the stability of the study drug and to ensure proper product identification, the drug product should not be stored in a container other than the container in which they are supplied. Consideration should be given to handling, preparation, and disposal through measures that minimize drug contact with the body. Appropriate precautions should be followed to avoid direct eye contact or exposure through inhalation when handling SOF/VEL tablets.

Sufficient quantities of SOF/VEL FDC tablets to complete the entire study will be shipped to the investigator or qualified designee from the Gilead Clinical Supply Management Team (or its designee).

## 5.2. Dosage and Administration of SOF/VEL FDC

SOF/VEL tablet is to be administered once daily with or without food. Each subject must be given instructions to maintain approximately the same daily dosing interval between study drug doses. If the subject is unable to swallow the SOF/VEL tablet, the tablet may be crushed and delivered by nasogastric tube.

For missed dose(s) of study medication, subjects should be instructed to take the missed dose of study medication as soon as possible during the same day. Subjects should be cautioned never to double the next dose with a missed dose of study drug under any circumstances.

## 5.3. Prior and Concomitant Medications

Concomitant medications taken within 30 days prior to Screening, up to and including 30 days after the last dose of study need to be recorded in the source documents and eCRFs.

The following medications are prohibited from **28 days prior to the Day 1** visit through the end of treatment:

- Investigational agents or devices for any indication

Concomitant use of certain medications or herbal/natural supplements (such as substrates, inhibitors or inducers of drug transporters or metabolizing enzymes, eg, P-gp or CYP3A) with the study drug may result in pharmacokinetic interactions resulting in increases or decreases in exposure of the study drug or these medications.

[Table 5-1](#) below contains medications that are prohibited from **21 days prior to Day 1** through the end of treatment and those medications that may be used with caution. The use of amiodarone is prohibited from **60 days prior to Day 1** through the end of treatment.

**Table 5-1. List of Disallowed /Use with Caution Medications**

Drug Class	Agents Disallowed	Use with Caution
Acid Reducing Agents a		Proton-Pump Inhibitors, H2-Receptor Antagonists, Antacids
Anticonvulsants b	Phenobarbital, Phenytoin, Carbamazepine, Oxcarbazepine	
Antimycobacterials b	Rifabutin, Rifapentine, Rifampin	
Cardiac Medications c	Amiodarone d	Diltiazem, Verapamil, Dronedaron, Quinidine, Ranolazine, Bosentan, Olmesartan, Valsartan, Digoxin e
Herbal/Natural Supplements b	St. John's Wort, Echinacea, Milk thistle (ie, silymarin), Chinese herb sho-saiko-to (or Xiao-Shai-Hu-Tang)	
HMG-CoA Reductase Inhibitors f		Rosuvastatin (≤10 mg/day)
Other	Modafinil b , Sulfasalazine c , Methotrexate c	

- a Proton pump inhibitor (PPI) doses comparable with omeprazole 20 mg can be administered with SOF/VEL when SOF/VEL is administered with food. H2-receptor antagonists must not exceed a dose of 40 mg famotidine or equivalent and can be taken simultaneously with SOF/VEL and/or staggered by 12 hours. Antacids that directly neutralize stomach acid (ie Tums, Maalox) may not be taken within 4 hours (before or after) of SOF/VEL administration.
- b May result in a decrease in the concentration of study drugs.
- c May result in an increase in the concentration of study drugs and/or concomitant medications
- d May result in symptomatic bradycardia. Mechanism is not currently known. The use of amiodarone is prohibited from 60 days prior to Baseline/Day 1 through the end of treatment
- e Monitor for signs and symptoms of digoxin toxicity.
- f Use with SOF/VEL may result in an increase in the concentration of HMG-CoA Reductase Inhibitors, rosuvastatin. Monitor for signs and symptoms of muscle weakness or myopathy, including rhabdomyolysis.

Medications for disease conditions **excluded** from the protocol (eg, HIV infection) are not listed under this Concomitant Medication section and are disallowed in the study.

Should subjects have a need to initiate treatment with any excluded concomitant medication, the Medical Monitor must be consulted prior to initiation of the new medication. In instances where an excluded medication is initiated prior to discussion with the Sponsor, the Investigator must notify Gilead as soon as he/she is aware of the use of the excluded medication.

#### 5.4. Accountability for SOF/VEL FDC

The investigator is responsible for ensuring adequate accountability of all used and unused study drug (SOF/VEL FDC). This includes acknowledgement of receipt of each shipment of study drug (quantity and condition). All used and unused study drug dispensed to subjects must be returned to the site.

SOF/VEL accountability records will be provided to each study site to:

- Record the date received and quantity of study drug shipments
- Record the date, subject number, subject initials, the study drug bottle number dispensed
- Record the date, quantity of used and unused IMP returned, along with the initials of the person recording the information.

Subjects must be instructed to bring back all study drugs in the original container at every post-Day 1 study visit through the end of treatment.

#### **5.4.1. Investigational Medicinal Product Return or Disposal**

Please refer to Section [9.1.7](#) for Investigational Medicinal Product Accountability and Return.

## **6. STUDY PROCEDURES**

The study procedures to be conducted for each subject enrolled in the study are presented in tabular form in [Appendix 2](#) and described in the text that follows. Additional information is provided in the study procedures manual.

The investigator must document any deviation from protocol procedures and notify the sponsor or contract research organization (CRO).

### **6.1. Subject Enrollment and Treatment Assignment**

### **6.2. Pretreatment Assessments**

#### **6.2.1. Screening Visit/Pre-Surgery**

Subjects will be initially screened to determine their eligibility for participation in the study (they are required to be on the waitlist for liver transplantation). If the screening visit occurs more than 48 hours before the liver transplant surgery is started, the subject will also be reassessed within 48 hours of transplantation to determine their continued eligibility at the pre-surgery visit.

Screening period is the time from initial screen (ie, identification of the subject as being on the liver transplant waitlist and potentially meeting inclusion/exclusion criteria for the study) until administration of the first dose of study treatment.

From the time of obtaining informed consent through the first administration of investigational medicinal product, record all serious adverse events (SAEs), as well as any adverse events related to protocol-mandated procedures on the adverse events case report form (eCRF). All other untoward medical occurrences observed during the screening period, including exacerbation or changes in medical history are to be captured on the medical history eCRF. See [Section 7 Adverse Events and Toxicity Management](#) for additional details.

#### **6.2.2. Day 1 Assessments**

Day 1 will be the morning following the transplant (if the subject is out of transplant before 12:00 pm the Day 1 dose will occur that day. If the subject is out of transplant after 12:00 pm the Day 1 dose will occur the following morning).

### **6.3. Treatment Assessments ( $\pm$ 2 days)**

Subjects meeting all of the inclusion and none of the exclusion criteria will begin study treatment on Day 1. In addition to those assessments listed in the Schedule of Events, study personnel will observe the subject taking their first dose of study drug and record the date and time the first dose was taken.

For all subjects receiving 4 weeks of therapy, treatment procedures/assessments are to be completed on Days 3, 5, 7, 14, 21, and 28 post start of Day 1 treatment. Please refer to [Appendix 2](#) for a schedule for assessments.

#### **6.4. Early Termination (ET) Visit**

For subjects who have completed an ET visit, the Post-treatment Weeks 1, 2, and 4, and 12 follow-up visits will be scheduled from the date of the last dose of study drug.

The sponsor (eg, Medical Monitor and Clinical Program Manager)/CRO must be informed as soon as possible if a subject discontinues treatment.

#### **6.5. Unscheduled Visits**

A subject should attend an unscheduled visit if requested by the sponsor or the investigator. The assessments are at the investigator's discretion as clinically indicated, but the investigator should at a minimum collect AE and concomitant medication information. At all unscheduled visits initiated for the purpose of confirming virologic failure a Viral RNA Sequencing/ Phenotyping Sample must be collected.

The Sponsor (eg, Medical Monitor and Clinical Program Manager)/CRO must be informed, as soon as possible, when a subject discontinues treatment.

#### **6.6. Post-Treatment Assessments**

Post-treatment Weeks 1, 2, 4, and 12 visits must be scheduled from the date of the last dose of study drug.

Subjects who have HCV RNA  $\leq$ LLOQ at end of treatment and do not relapse will complete all post-treatment visits at Weeks 1, 2, 4, and 12. Subjects that experience relapse will have confirmatory testing as soon as possible and will not be required to complete additional visits.

If a subject must undergo a second transplantation while on study treatment or is relisted for transplantation, all study treatment must be stopped.

If a subject is in the Post-treatment follow-up and undergoes a second liver transplant, the subject will continue with the follow-up visits from the first transplantation (for the assessment of Post-transplant recurrence). If the subject is more than 4 weeks after the last dose of study drug at the time of the second transplant and had completed the safety follow-up period, it is not necessary to resume adverse event collection.

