### **3.7. End of Study**

Subjects are considered to have completed the study after the Post-treatment Week 12 follow-up visit, regardless of treatment duration, unless the subject early terminates because HCV RNA is  $\geq$  LLOQ. If the subject terminates early due to HCV RNA  $\geq$  LLOQ, the subject will complete the post treatment Week 4 visit as their final visit.

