## 6.8. End of Study

Subjects are considered to have completed the study after the post-treatment Week 12 visit, regardless of treatment duration or early termination of study drug. If the subject terminates early due to HCV RNA  $\geq$  LLOQ, the subject may discontinue follow up after the post treatment Week 4 visit.

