#### Adverse Events

All AEs, except those described in Section 7.5, regardless of cause or relationship, that occur from initiation of study medication until 30-days after last administration of study drug must be reported to the eCRF database as instructed.

All AEs should be followed up until resolution or until the adverse event is stable, if possible. Gilead Sciences may request that certain AEs be followed beyond the protocol defined follow up period.

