### **8.1.4. Safety Endpoint**

The primary safety endpoint is any AE leading to premature discontinuation of study drug. Other important safety endpoints include deaths, graft losses, and rejection episodes.

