#### **8.2.1.2. Safety**

The analysis set for safety analyses will include all subjects who took at least one dose of study drug.

All safety data collected from the first dose of any study drug (including the perioperative dose of SOF/VEL) through the date of last dose of study drug plus 30 days will be included in safety summaries, unless otherwise specified.

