Subjects will be treated for 4 weeks and followed off-treatment for 12 weeks. All subjects will be eligible to participate in the PG substudy if consent is obtained. A blood sample should be drawn at the Day 1 visit. If not obtained at the Day 1 visit, the sample may be drawn at any time during the study.

Subjects with VF (either at end of treatment or during follow-up) will have a confirmation sample collected. If VF is confirmed, the subject will be discontinued from study.

Subjects who prematurely discontinue from study drug but complete all posttreatment visits will be considered to have completed study.

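### The exit rules for virologic failure conflict: Protocol 3.7 and 6.8 keep the post-treatment Week 4 safety visit, Protocol 6.6 and SAP 1.2 do not

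*Protocol*

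**What the plan says.** Four passages state when a subject with HCV RNA at or above LLOQ leaves the study.

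- Protocol 3.7, on early termination for that reason: "the subject will complete the post treatment Week 4 visit as their final visit".
- Protocol 6.8, same trigger: "the subject may discontinue follow up after the post treatment Week 4 visit".
- Protocol 6.6: "Subjects that experience relapse will have confirmatory testing as soon as possible and will not be required to complete additional visits".
- SAP 1.2, for virologic failure at end of treatment or in follow-up, after a confirmation sample: "If VF is confirmed, the subject will be discontinued from study".

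The safety plan runs to about four weeks after the last dose. The synopsis (Criteria for Evaluation) plans adverse events and safety laboratory tests through the post-treatment Week 4 visit. Protocol 7.3 covers events "that occur from initiation of study medication until 30-days after last administration of study drug must be reported", with the same period for serious events. Protocol 8.2.1.2 states that data "through the date of last dose of study drug plus 30 days will be included in safety summaries".

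Appendix Table 2 schedules HCV RNA at post-treatment Weeks 1, 2, 4 and 12. Adverse events are scheduled at Weeks 1, 2 and 4, and vital signs at Week 4 only.

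**The concern.** HCV RNA is drawn at post-treatment Weeks 1 and 2, so failure can be found and confirmed before Week 4. Two passages then keep the subject to Week 4 and two release the subject sooner. Week 4 is the last scheduled adverse-event collection. It is also the last scheduled laboratory draw that SAP Table 2 admits to the safety summaries, because the Week 12 laboratory results are not summarised.

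The loss would be selective. Week 4 ALT, AST and bilirubin in a new graft would be summarised without the subjects whose infection came back early. Protocol 6.7 points to Section 6.6 for the required follow-up, so the waiver is not in an obscure place. Section 6.6 itself refers, in its text on second transplants, to a safety follow-up period of four weeks.

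Early failure is not remote. In the genotype 3 study summarised in Protocol 1.6, 8 of 11 relapses on SOF/VEL had occurred by post-treatment Week 4. That was a different population, and the count may include relapses found at the Week 4 visit.

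**Working it through.** **1. The rules side by side**

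| Place | Trigger | Consequence | Week 4 kept? |
|---|---|---|---|
| Protocol 3.7 | Early termination, HCV RNA ≥ LLOQ | Week 4 is the final visit | Yes, required |
| Protocol 6.8 | Same | Follow-up may stop after Week 4 | Yes, as earliest exit |
| Protocol 6.6 | Relapse, with confirmatory test | No further visit required | No minimum |
| SAP 1.2 | Confirmed failure, end of treatment or follow-up | Discontinued from study | No minimum |

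The drug-stopping lists in Protocol 3.5 and 3.6 contain no virologic criterion, and 3.7 and 6.8 are both End of Study sections. Their trigger is therefore most naturally read as study exit for viremia. SAP 1.2 covers both kinds of failure, so it overlaps with them on any reading.

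**2. Visit windows (Appendix Table 2, days after last dose)**

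- Week 1: 7 ± 3 = Day 4 to 10
- Week 2: 14 ± 3 = Day 11 to 17
- Week 4: 28 ± 5 = Day 23 to 33

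**3. Days up to Day 30 without a scheduled visit = 30 − exit day**

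- Exit at the Week 1 visit: 30 − 10 = 20 to 30 − 4 = 26. This fits end-of-treatment viremia confirmed at that visit, under SAP 1.2.
- Exit at the Week 2 visit: 30 − 17 = 13 to 30 − 11 = 19. This fits a relapse seen at Week 1 and confirmed at Week 2.
- For comparison, a compliant Week 4 visit on Day 23 leaves 30 − 23 = 7 days.

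Net coverage lost is min(Week 4 day, 30) − exit day. For a Week 1 exit this is 23 − 10 = 13 to 30 − 4 = 26 days. For a Week 2 exit it is 23 − 17 = 6 to 30 − 11 = 19 days.

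**4. Confirmation at an unscheduled visit**

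The documents give no fixed delay, so 0, 3 and 7 days are assumed. Exit day = day of the positive sample + delay.

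| Positive sample | Delay | Exit day | Days left to Day 30 |
|---|---|---|---|
| Last dosing day (Day 0) | 0 / 3 / 7 | 0 / 3 / 7 | 30 / 27 / 23 |
| Week 1 | 0 / 3 / 7 | 4–10 / 7–13 / 11–17 | 20–26 / 17–23 / 13–19 |
| Week 2 | 0 / 3 / 7 | 11–17 / 14–20 / 18–24 | 13–19 / 10–16 / 6–12 |

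Every exit falls before Day 23 except the latest Week 2 cases with a 7-day delay (Days 23 and 24).

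**5. Laboratory summary**

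SAP Table 2 assigns laboratory data on Day 21 to 30 to FU-4. Results from Day 4 to 20 go to FU-1 or FU-2. Protocol 8.3 leaves a subject without a result out of that time point. One such subject is 1/10 = 10% of the planned number.

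**The case against.** **Triggers differ.** Protocol 3.7 and 6.8 speak of early termination for viremia, while 6.6 speaks of relapse. The first pair could be meant for subjects still viremic at end of treatment, for whom 6.6 gives no rule. Also, 6.6 waives visits without forbidding them. This stands, and it makes the conflict inside the protocol arguable. It does not remove the conflict with SAP 1.2, which is worded as a discontinuation and covers both groups. The SAP is not the document that sites follow for visits, but it says that it is based on the protocol and lists no revision that would explain the difference.

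**Adverse events are still reported.** A reader might infer that the 30-day window is shortened. It is not: the duty in Protocol 7.3 has no exception for relapse. At an unscheduled visit, "the investigator should at a minimum collect AE and concomitant medication information". The days counted above are days without a scheduled visit, not days without reporting.

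**Vital signs.** A reader might infer a 10% loss in the Week 4 vital-sign summary. The documents do not support this in general. SAP Table 2 assigns vital signs from Day 4 to 30 to FU-4, and the ET/Unscheduled column of Appendix Table 1 lists vital signs and laboratory tests. A confirmation visit from Day 4 can therefore supply the value, although Protocol 6.5 leaves assessments beyond adverse events and medications to the investigator.

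**Laboratory tests.** A sample from an unscheduled visit on Day 21 to 30 fills the FU-4 window. Conversely, a compliant Week 4 visit on Day 31 to 33 falls outside it, so the early exit rule is not the only way to lose a FU-4 result.

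**Disposition.** A reader might infer that completion counts move by 10 points with the passage followed. Protocol 6.8 ties completion to Week 12 and SAP 1.2 calls the exit a discontinuation, so both point to not completed, whether exit is before or after Week 4. Only the *unless* clause in Protocol 3.7 clouds this.

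**SVR12.** A reader might infer that the SAP leaves SVR12 open for these subjects. It does not. Protocol 8.3 counts them as failures at later visits, and SAP 3.6.1 treats a missing post-treatment value that is not bracketed by successes as a failure.

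**Conclusion.** The inconsistency is real and should be corrected, but its effect is limited. SAP 1.2 conflicts firmly with Protocol 3.7 and 6.8; Protocol 6.6 conflicts on the natural reading. Followed as written, SAP 1.2 or Protocol 6.6 allows exit with 13 to 26 of the 30 safety days lacking a scheduled visit when exit is at the Week 1 or Week 2 visit. With confirmation at an unscheduled visit, the figure depends on the assumed delay. The FU-4 laboratory summary loses one tenth of the planned subjects for each such exit without a sample on Day 21 to 30. The documents do not say how many subjects this concerns.

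Efficacy is untouched: SVR4 and SVR12 are failures by rule. The primary safety endpoint is essentially unaffected, because it concerns events that stop treatment: "The primary safety endpoint is any AE leading to premature discontinuation of study drug".

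**What to change.** Reconcile Protocol 3.7, 6.6 and 6.8 and SAP 1.2 into one data-collection rule, worded the same in both documents and consistent with the 30-day safety period in the synopsis and Protocol 7.3 and 8.2.1.2. One way is to retain the already scheduled Week 4 safety visit, or an adverse-event contact at Day 30, whatever the HCV RNA result.

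Reword the *unless* clause in Protocol 3.7 so that exit on virologic failure has a single status in the disposition table of SAP 4.1.3.

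SAP 3.1.2 reads as if written after all subjects had been dosed. If follow-up is already over, list each subject who left before Week 4, with exit day and date of last adverse-event assessment.

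The cost is wording edits, plus either one already scheduled visit or contact for each affected subject, or one short listing.
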